### **8.2.4 Electrocardiograms and Echocardiograms**

A single 12-lead ECG will be done during the screening period and at Day 14 or upon discharge from the hospital. The ECG should be collected during the treatment period, as clinically indicated per SoA (Table 1). For all ECGs, details of rhythm, ECG intervals, and an overall evaluation will be recorded.

An echocardiogram should be collected at screening or during the treatment period, as clinically indicated per SoA (Table 1). Percentage left ventricular ejection fraction should be recorded.

If the Investigator considers an abnormal ECG or echocardiogram finding at screening or baseline to be clinically significant, that finding should be reported as a concurrent condition.

Any clinically significant abnormal ECG or echocardiogram findings during the treatment period should be recorded in the source document and the AE section of eCRF, according to standard AE collection and reporting processes.

### **8.2.5 Clinical Safety Laboratory Assessments**

#### **8.2.5.1 Local Laboratory Tests**

The following laboratory tests will be done as specified in the SoA (Table 1) using the site's local laboratories:

- Hematology studies must include complete blood count with differential including, but not limited to white blood cell count, hemoglobin, platelet count, absolute neutrophil count or percentage, red blood cell count, absolute monocyte count or percentage, and absolute lymphocyte count or percentage.
- Serum or plasma chemistry will include albumin, ALP, ALT, AST, bicarbonate, blood urea nitrogen, calcium, chloride, creatinine, glucose, lactate dehydrogenase, magnesium,

phosphate, potassium, sodium, TBL (direct and indirect bilirubin, if available), total protein, and uric acid.

- Urine or serum pregnancy testing (women of childbearing potential only; Appendix F)
- C-reactive protein
- Fibrinogen, D-dimer\*
- Prothrombin time, aPTT, INR\*
- Cardiac troponin I\*
- Hepatitis serology must include, at a minimum, HBsAg, anti-HBc, and HCV antibody (if additional hepatitis serology is collected per institutional guidelines, it should be recorded in the database) (see hepatitis serology guidelines in Section 8.2.5.1.1)
- SARS-CoV-2 reverse transcriptase-polymerase chain reaction viral test. Sites should report this as positive/negative.

\*These laboratory tests should be performed more frequently than described in the SoA (Table 1), if clinically indicated.

**NOTE:** Safety and CRP laboratory tests are considered Tier 1 and should not be missed. The site must follow the SoA.

**NB.** In case a participant shows an AST **or** ALT  $\geq 3 \times$  ULN together with TBL  $\geq 2 \times$  ULN, refer to Appendix D for actions required in cases of increases in liver biochemistry and evaluation of Hy's Law'.

#### 8.2.5.1.1 Hepatitis Serology Guidelines

If feasible, hepatitis serology data should be obtained prior to administration of the first dose. However, if not feasible, sites should proceed as described below.

Participants must not meet Exclusion Criterion 9 (see Section 5.2):

- Known active hepatitis B or C infection as determined by active treatment
- Medical history or any routine clinical or laboratory evidence, that in the judgement of the Investigator, suggests chronic or active viral hepatitis.

Blood samples for all HBV and HCV serology tests, and for both HBV and HCV PCR tests must then be collected **before** administration of the first dose.

- If results become available before administration of the first dose, participants with positive HBsAg, HBV-DNA, or HCV-RNA test results will be excluded and should be treated per institutional guidelines.

- Participants who are anti-HBc positive and who are HBsAg negative will need to have a negative or undetectable hepatitis B viral load (HBV-DNA) by quantitative PCR result.
- Participants who are HCV antibody positive will need to have a negative PCR.
- If results are not available at the time of first dose administration, participants can be started on acalabrutinib. If any of the HBsAg, HBV-DNA, or HCV-RNA test results are positive after the first dose, the following must occur:
  - Discontinue further treatment with acalabrutinib.
  - Withdraw the participant from the study.
  - Modify BSC as clinically indicated per Investigator judgement.
  - Initiate a monitoring and therapeutic plan for HBV/HCV infection according to institutional guidelines and Investigator judgement.

### 8.2.5.2 Central Laboratory Tests

Samples will be collected as specified in the SoA (Table 1) and sent to a central laboratory for the following laboratory tests:

- Plasma samples for acalabrutinib/ACP-5862 PK

**NOTE:** PK, [REDACTED] are considered Tier 1 and should not be missed. The site must follow the SoA.

Refer to the Laboratory Manual for instructions on processing and shipping. Additional handling information is provided in Appendix C.

## 8.3 Adverse Events and Serious Adverse Events

The Principal Investigator is responsible for ensuring that all staff involved in the study are familiar with the content of this section

The definitions of an AE or SAE can be found in Appendix B.

Adverse events will be reported by the participant (or, when appropriate, by a caregiver, surrogate, or the participant's legally authorized representative).

The Investigator and any designees are responsible for detecting, documenting, and recording events that meet the definition of an AE.

### **8.3.1 Time Period and Frequency for Collecting AE and SAE Information**

Adverse events will be collected from the time of signature of the ICF through 28 ( $\pm$  3) days after the last dose of study intervention.

Serious adverse events will be recorded from the time of signing the ICF.

If the Investigator becomes aware of an SAE with a suspected causal relationship to the study intervention that occurs after the end of the clinical study in a participant treated by him or her, the Investigator shall, without undue delay, report the SAE to the Sponsor.

### **8.3.2 Follow-up of AEs and SAEs**

Any AEs that are unresolved at the participant's last AE an assessment in the study are followed up by the Investigator for as long as medically indicated, but without further recording in the eCRF. The Sponsor retains the right to request additional information for any participant with ongoing AE(s)/SAE(s) at the end of the study, if judged necessary.

#### **Adverse event variables**

The following variables will be collected for each AE:

- Adverse event (verbatim)
- The date and time when the AE started and stopped
- The CTCAE grade and grade changes, with the date they changed
- Whether the AE is serious or not
- Investigator causality rating against the study intervention (yes or no)
- Action taken with regard to study intervention
- Outcome

In addition, the following variables will be collected for SAEs:

- Date AE met criteria for SAE
- Date Investigator became aware of SAE
- Adverse event is serious due to
- Date of hospitalization
- Date of discharge
- Probable cause of death

- Date of death
- Autopsy performed
- Causality assessment in relation to study procedure(s)
- Causality assessment to other medication

### **8.3.3 Causality Collection**

The Investigator should assess causal relationship between study intervention and each AE, and answer ‘yes’ or ‘no’ to the question ‘Do you consider that there is a reasonable possibility that the event may have been caused by the study intervention?’

For SAEs, causal relationship should also be assessed for other medication and study procedures. Note that for SAEs that could be associated with any study procedure the causal relationship is implied as ‘yes’.

A guide to the interpretation of the causality question is found in Appendix B.

### **8.3.4 Adverse Events Based on Signs and Symptoms**

All AEs spontaneously reported by the participant or reported in response to the open question from the study site staff: ‘Have you/the child had any health problems since the previous visit/you were last asked?’, or revealed by observation will be collected and recorded in the eCRF. When collecting AEs, the recording of diagnoses is preferred (when possible) to recording a list of signs and symptoms. However, if a diagnosis is known and there are other signs or symptoms that are not generally part of the diagnosis, the diagnosis and each sign or symptom will be recorded separately.

### **8.3.5 Adverse Events Based on Examinations and Tests**

The results from the CSP mandated laboratory tests and vital signs will be summarized in the CSR.

Deterioration as compared to baseline in protocol-mandated laboratory values and vital signs should therefore only be reported as AEs if they fulfil any of the SAE criteria, are the reason for discontinuation of treatment with the study intervention or are considered to be clinically relevant as judged by the Investigator (which may include but not limited to consideration as to whether treatment or non-planned visits were required or other action was taken with the study intervention, eg, dose adjustment or drug interruption).

If deterioration in a laboratory value/vital sign is associated with clinical signs and symptoms, the sign or symptom will be reported as an AE and the associated laboratory result/vital sign will be considered as additional information. Wherever possible, the reporting Investigator uses the clinical, rather than the laboratory term (eg, anemia versus low hemoglobin value). In

the absence of clinical signs or symptoms, clinically relevant deteriorations in non-mandated parameters should be reported as AE(s).

Deterioration of a laboratory value, which is unequivocally due to disease progression, should not be reported as an AE/SAE.

Any new or aggravated clinically relevant abnormal medical finding at a physical examination as compared with the baseline assessment will be reported as an AE unless unequivocally related to the disease under study.

### **8.3.6 Hy's Law**

Cases where a participant shows elevations in liver biochemistry may require further evaluation and occurrences of AST or ALT  $\geq 3 \times$  ULN together with TBL  $\geq 2 \times$  ULN may need to be reported as SAEs. Please refer to Appendix D for further instruction on cases of increases in liver biochemistry and evaluation of Hy's Law.

### **8.3.7 Disease Progression**

Disease progression can be considered as a worsening of a participant's condition attributable to COVID-19 pneumonia for which the study intervention is being studied. It may be an increase in the severity of the disease under study and/or increases in the symptoms of the disease. Events, which are unequivocally due to COVID-19 pneumonia, should not be reported as an AE or SAE during the study. Events attributable to disease progression of COVID-19 include pulmonary failure, acute respiratory distress syndrome, sepsis, shock, multiorgan failure and death.

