### **8.3.8 Disease Under study**

Systemic symptoms of the disease under study are those that might be expected to occur as a direct result of the clinical presentation associated with COVID-19 pneumonia and respiratory illness. Events which are unequivocally due to disease under study should not be reported as an AE during the study unless they meet SAE criteria or lead to discontinuation of the study intervention.

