### **8.3.9 Reporting of Serious Adverse Events**

All SAEs have to be reported, whether or not considered causally related to the study intervention, or to the study procedure(s). All SAEs will be recorded in the eCRF.

If any SAE occurs in the course of the study, then Investigators or other site personnel inform the appropriate Sponsor representatives within one day ie, immediately but **no later than 24 hours** of when he or she becomes aware of it.

The designated Sponsor representative works with the Investigator to ensure that all the

necessary information is provided to the Sponsor Patient Safety data entry site **within 1 calendar day** of initial receipt for fatal and life-threatening events **and within 5 calendar days** of initial receipt for all other SAEs.

For fatal or life-threatening AEs where important or relevant information is missing, active follow-up is undertaken immediately. Investigators or other site personnel inform Sponsor representatives of any follow-up information on a previously reported SAE within 1 calendar day, ie, immediately but **no later than 24 hours** of when he/she becomes aware of it.

For all studies except those utilizing medical devices, Investigator safety reports must be prepared for SUSARs according to local regulatory requirements and Sponsor policy and forwarded to Investigators as necessary.

An Investigator who receives an Investigator safety report describing an SAE or other specific safety information (eg, summary or listing of SAEs) from the Sponsor will review and file the report/information with the IB and will notify the IRB/IEC according to local requirements, if appropriate.

Refer to Appendix B for further guidance on the definition of a SAE.

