### 9.6 Safety Review Committee

This study will have an SRC. The SRC will conduct scheduled reviews of safety and other relevant data. In addition, The SRC will meet to review any of the following events should they occur during the study:

- Any death due to acalabrutinib (per Investigator)
- Any Grade 4 hemorrhage due to acalabrutinib (per Investigator)

The SRC will consist of the AstraZeneca Study Physician or delegate, Principal Investigator or equivalent delegate from active investigational sites, and Global Safety Physician or delegate. Other attendees may also be invited as appropriate.

Details on the process of ongoing evaluation of safety data by the SRC and the committee composition is described further in the SRC charter.

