### **B 2 Definitions of Serious Adverse Event**

A serious adverse event is an AE occurring during any study phase (ie, run-in, treatment, washout, follow-up), that fulfils one or more of the following criteria:

- Results in death
- Is immediately life-threatening
- Requires in-participant hospitalisation or prolongation of existing hospitalisation
- Results in persistent or significant disability or incapacity.
- Is a congenital abnormality or birth defect
- Is an important medical event that may jeopardise the participant or may require medical treatment to prevent one of the outcomes listed above.

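### Sections 8.3.7 and 8.3.8 give opposite instructions on reporting serious events judged unequivocally due to COVID-19, so the SAE component of a primary endpoint depends on which section a site follows

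*Protocol*

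**What the plan says.** Four places in the protocol bear on this.

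- **Section 8.3.7 (Disease Progression):** "Events, which are unequivocally due to COVID-19 pneumonia, should not be reported as an AE or SAE during the study". The next sentence reads: "Events attributable to disease progression of COVID-19 include pulmonary failure, acute respiratory distress syndrome, sepsis, shock, multiorgan failure and death". There is no exception for seriousness or for events that end treatment.
- **Section 8.3.8 (Disease Under study):** "Events which are unequivocally due to disease under study should not be reported as an AE during the study unless they meet SAE criteria". A second exception follows, for events that lead to discontinuation of study intervention.
- **Section 8.3.9 (SAE reporting)** sets this rule: "All SAEs have to be reported, whether or not considered causally related to the study intervention, or to the study procedure(s". Sites must inform the sponsor within 24 hours.
- **Appendix B 2:** the SAE criteria include "Results in death" and immediate threat to life. Disease progression is not excluded.

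SAEs and AEs leading to discontinuation are named in the endpoint for the second primary objective (Table 3). Section 9.1 states that safety endpoints are not formally tested. Section 8.3.2 lists items collected only for SAEs, among them probable cause of death, whether an autopsy was done, and causality in relation to other medication.

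**The concern.** Sections 8.3.7 and 8.3.8 are adjacent, both are current text, and both are triggered by an event being unequivocally due to the disease. For a serious event they then point in opposite directions. A site following 8.3.7 files nothing for a death it is certain was COVID-19. A site following 8.3.8 files an SAE for the same death.

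Safety is a primary objective, and section 2.3.1.2 lists serious and fatal infection as a risk of acalabrutinib, while section 8.3.7 names sepsis as disease progression. The study has one open-label arm, so no comparator would later show whether attribution had been applied evenly. If sites read the rule differently, the pooled SAE and discontinuation-AE tables mix two definitions, and a reader cannot tell how many events were left out.

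**Working it through.** The point is textual and the plan gives no figure to reproduce. The rules are compared first, and the possible size follows as an illustration.

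**Step 1. One event under each rule.** Take a death that the investigator judges unequivocally due to COVID-19 pneumonia.

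| Place | Instruction |
|---|---|
| 8.3.7 | Not reported as AE or SAE |
| 8.3.8 | Reported, because it meets SAE criteria |
| 8.3.9 | SAEs are reported whatever their causal relation to study treatment or procedures; disease progression not mentioned |
| Appendix B 2 | Death is an SAE criterion; no exclusion for progression |

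Life-threatening sepsis, shock or multiorgan failure gives the same result, through the life-threatening criterion.

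**Step 2. A disease event that ends treatment.** Under 8.3.8 it is reported even if not serious. Under 8.3.7 it is not. The discontinuation-AE component is therefore affected as well.

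**Step 3. Does another passage settle it?** None does.

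- Section 8.3.5 follows the 8.3.7 approach, but only for laboratory values.
- Appendix B 3 tells investigators how to code causality when the disease has worsened through lack of effect, and Table 7 speaks of Grade 4 AEs that are not COVID-19-related. Both suggest that some disease-related events are expected to be recorded as AEs.
- Neither amendment log addresses the difference.

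**Step 4. Possible size for deaths (illustration only).**

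Inputs:
- n = 20, the approximate planned enrolment (section 9.2), here all assumed treated.
- Mortality p from 0.25 to 0.50. The upper end is close to the figure in section 2.2.1 for ventilated patients. The lower end is an assumption, made because high-flow oxygen and non-invasive ventilation also qualify (inclusion criterion 4).

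Expected deaths D = n × p:
- p = 0.25: 20 × 0.25 = 5 (binomial 5th to 95th percentile 2 to 8)
- p = 0.50: 20 × 0.50 = 10 (6 to 14)

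The chance of at least one death is 1 − (1 − p)^20. At p = 0.25 this is 1 − 0.75^20 = 0.997, and it is higher at larger p. The rule will almost certainly be needed.

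Let q be the share of deaths that are both judged unequivocally due to COVID-19 and handled by a site following 8.3.7. Fatal SAEs counted = D × (1 − q).
- q = 0: 5 to 10, or 5/20 = 25% to 10/20 = 50%
- q = 1: 0

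The difference of up to 25 to 50 percentage points needs q = 1, so it is an upper bound. The protocol gives no basis for estimating q, or for a similar count of sepsis, shock or organ failure.

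**The case against.** **The two sections may have different scopes.** Section 8.3.7 opens with worsening of the disease and 8.3.8 with presenting systemic symptoms. This is the best defence, and it narrows the overlap without removing it. The operative sentence of 8.3.8 covers events due to the disease in general, and symptoms alone would seldom meet SAE criteria. A COVID-19 death fits both triggers.

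**Section 8.3.7 may be an exception to 8.3.9.** This largely stands. Section 8.3.9 concerns causal relation to study treatment and procedures, and 8.3.7 could be read as carving progression out of it. The firm conflict is between 8.3.7 and 8.3.8. Section 8.3.9 and Appendix B 2 contribute only that they state no such exception.

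**Deaths are recorded elsewhere.** This stands. Table 1 collects survival status at Day 14 or discharge, Day 20, Day 28 and safety follow-up. Death is score 8 in Table 8, and survival is part of a secondary endpoint at Days 14 and 28. Organ function is also scored by mSOFA up to Day 14 or discharge. A reader might infer that deaths vanish from the trial; the documents do not support that.

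**Only unequivocal events are affected.** This also stands. A reader might infer that 8.3.7 strips out the very events in which a drug effect would show. But an event that cannot be separated from a drug effect is not unequivocally due to COVID-19 and stays reportable under 8.3.7. The risk is limited to misplaced certainty and uneven reading between sites.

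**The Safety Review Committee.** A reader might add that its event-driven trigger, "Any death due to acalabrutinib (per Investigator"), suffers from the same fault. That trigger comes on top of scheduled reviews of safety data (section 9.6), and it contradicts nothing. It is not part of this point.

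**Conclusion.** The contradiction between 8.3.7 and 8.3.8 is real and unresolved in the current text. It concerns serious events, and events ending treatment, that are judged unequivocally due to COVID-19. For these, the section a site follows decides three things: entry into the SAE and discontinuation-AE tables, 24-hour reporting, and collection of SAE-only details such as probable cause of death.

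For fatal SAEs the difference is at most about 5 to 10 of 20 participants against none. That bound assumes 20 treated, 25% to 50% mortality and every death judged unequivocally due to COVID-19. The true difference would be smaller if some attributions were uncertain or some sites followed 8.3.8.

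The endpoint is one of two primary objectives and is descriptive, so no error rate or power is affected. The correction is still needed, because the content of a primary endpoint should not vary by site.

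**What to change.** Reconcile sections 8.3.7, 8.3.8, 8.3.9 and Appendix B 2 into one rule, state it once, cross-refer to it from the others, and apply it at all sites. The choice of rule is the sponsor's.

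A low-cost option that discards nothing:

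- Record every event that meets SAE criteria, deaths included, or that leads to discontinuation of study treatment on the AE/SAE eCRF.
- Add one yes/no field for attribution to COVID-19 progression.
- Tabulate SAEs, deaths and discontinuation AEs overall and by that field, so that the view without progression events remains available.

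The cost is a wording amendment, one eCRF field and more SAE pages. Reported SAE rates will look higher than under 8.3.7, and the split by flag lets a reader see why.

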### **8.3.8 Disease Under study**

Systemic symptoms of the disease under study are those that might be expected to occur as a direct result of the clinical presentation associated with COVID-19 pneumonia and respiratory illness. Events which are unequivocally due to disease under study should not be reported as an AE during the study unless they meet SAE criteria or lead to discontinuation of the study intervention.

### **8.3.9 Reporting of Serious Adverse Events**

All SAEs have to be reported, whether or not considered causally related to the study intervention, or to the study procedure(s). All SAEs will be recorded in the eCRF.

If any SAE occurs in the course of the study, then Investigators or other site personnel inform the appropriate Sponsor representatives within one day ie, immediately but **no later than 24 hours** of when he or she becomes aware of it.

The designated Sponsor representative works with the Investigator to ensure that all the

necessary information is provided to the Sponsor Patient Safety data entry site **within 1 calendar day** of initial receipt for fatal and life-threatening events **and within 5 calendar days** of initial receipt for all other SAEs.

For fatal or life-threatening AEs where important or relevant information is missing, active follow-up is undertaken immediately. Investigators or other site personnel inform Sponsor representatives of any follow-up information on a previously reported SAE within 1 calendar day, ie, immediately but **no later than 24 hours** of when he/she becomes aware of it.

For all studies except those utilizing medical devices, Investigator safety reports must be prepared for SUSARs according to local regulatory requirements and Sponsor policy and forwarded to Investigators as necessary.

An Investigator who receives an Investigator safety report describing an SAE or other specific safety information (eg, summary or listing of SAEs) from the Sponsor will review and file the report/information with the IB and will notify the IRB/IEC according to local requirements, if appropriate.

Refer to Appendix B for further guidance on the definition of a SAE.

